## Informed Consent

Subjects who do not wish to participate in the genetic research may still participate in the study. Genetic informed consent must be obtained prior to any blood being taken.

## Subject Withdrawal from Study

If a subject who has consented to participate in genetic research withdraws from the clinical study for any reason other than being lost to follow-up, the subject will be given a choice of one of the following options concerning the genetic sample, if already collected:

- Continue to participate in the genetic research in which case the genetic DNA sample is retained
- Discontinue participation in the genetic research and destroy the genetic DNA sample

If a subject withdraws consent for genetic research or requests sample destruction for any reason, the investigator must complete the appropriate documentation to request sample

destruction within the timeframe specified by GSK and maintain the documentation in the site study records.

Genotype data may be generated during the study or after completion of the study and may be analyzed during the study or stored for future analysis.

- If a subject withdraws consent for genetic research and genotype data has not been analyzed, it will not be analyzed or used for future research.
- Genetic data that has been analyzed at the time of withdrawn consent will continue to be stored and used, as appropriate.

### **Screen and Baseline Failures**

If a sample for genetic research has been collected and it is determined that the subject does not meet the entry criteria for participation in the study, then the investigator should instruct the subject that their genetic sample will be destroyed. No forms are required to complete this process as it will be completed as part of the consent and sample reconciliation process. In this instance a sample destruction form will not be available to include in the site files.

### **Provision of Study Results and Confidentiality of Subject's Genetic Data**

GSK may summarize the genetic research results in the clinical study report, or separately and may publish the results in scientific journals.

GSK may share genetic research data with other scientists to further scientific understanding in alignment with the informed consent. GSK does not inform the subject, family members, insurers, or employers of individual genotyping results that are not known to be relevant to the subject's medical care at the time of the study, unless required by law. This is due to the fact that the information generated from genetic studies is generally preliminary in nature, and therefore the significance and scientific validity of the results are undetermined. Further, data generated in a research laboratory may not meet regulatory requirements for inclusion in clinical care.

## 14.6. Appendix 6: Definition of and Procedures for Recording, Evaluating, Follow-Up and Reporting of Adverse Events

### 14.6.1. Definition of Adverse Events

#### Adverse Event Definition:

- An AE is any untoward medical occurrence in a patient or clinical investigation subject, temporally associated with the use of a medicinal product, whether or not considered related to the medicinal product.
- NOTE: An AE can therefore be any unfavorable and unintended sign (including an abnormal laboratory finding), symptom, or disease (new or exacerbated) temporally associated with the use of a medicinal product.

#### Events meeting AE definition include:

- Any abnormal laboratory test results (hematology, clinical chemistry, or urinalysis) or other safety assessments (e.g., ECGs, radiological scans, vital signs measurements), including those that worsen from baseline, and felt to be clinically significant in the medical and scientific judgement of the investigator.
- Exacerbation of a chronic or intermittent pre-existing condition including either an increase in frequency and/or intensity of the condition.
- New conditions detected or diagnosed after study treatment administration even though it may have been present prior to the start of the study.
- Signs, symptoms, or the clinical sequelae of a suspected interaction.
- Signs, symptoms, or the clinical sequelae of a suspected overdose of either study treatment or a concomitant medication (overdose per se will not be reported as an AE/SAE unless this is an intentional overdose taken with possible suicidal/self-harming intent. This should be reported regardless of sequelae).
- "Lack of efficacy" or "failure of expected pharmacological action" per se will not be reported as an AE or SAE. However, the signs and symptoms and/or clinical sequelae resulting from lack of efficacy will be reported if they fulfil the definition of an AE or SAE.
- The signs and symptoms and/or clinical sequelae resulting from lack of efficacy will be reported if they fulfil the definition of an AE or SAE. Also, "lack of efficacy" or "failure of expected pharmacological action" also constitutes an AE or SAE.

**Events NOT meeting definition of an AE include:**

- Any clinically significant abnormal laboratory findings or other abnormal safety assessments which are associated with the underlying disease, unless judged by the investigator to be more severe than expected for the subject's condition.
- The disease/disorder being studied or expected progression, signs, or symptoms of the disease/disorder being studied, unless more severe than expected for the subject's condition.
- Medical or surgical procedure (e.g., endoscopy, appendectomy): the condition that leads to the procedure is an AE.
- Situations where an untoward medical occurrence did not occur (social and/or convenience admission to a hospital).
- Anticipated day-to-day fluctuations of pre-existing disease(s) or condition(s) present or detected at the start of the study that do not worsen.

**14.6.2. Definition of Serious Adverse Events**

If an event is not an AE per definition above, then it cannot be an SAE even if serious conditions are met (e.g., hospitalization for signs/symptoms of the disease under study, death due to progression of disease, etc).

**Serious Adverse Event (SAE) is defined as any untoward medical occurrence that, at any dose:**

**a. Results in death****b. Is life-threatening**

NOTE:

The term 'life-threatening' in the definition of 'serious' refers to an event in which the subject was at risk of death at the time of the event. It does not refer to an event, which hypothetically might have caused death, if it were more severe.

**c. Requires hospitalization or prolongation of existing hospitalization**

NOTE:

- In general, hospitalization signifies that the subject has been detained (usually involving at least an overnight stay) at the hospital or emergency ward for observation and/or treatment that would not have been appropriate in the physician's office or out-patient setting. Complications that occur during hospitalization are AEs. If a complication prolongs hospitalization or fulfills any other serious criteria, the event is serious. When in doubt as to whether "hospitalization" occurred or was necessary, the AE should be considered serious.
- Hospitalization for elective treatment of a pre-existing condition that did not worsen from baseline is not considered an AE.

**d. Results in disability/incapacity**

## NOTE:

- The term disability means a substantial disruption of a person's ability to conduct normal life functions.
- This definition is not intended to include experiences of relatively minor medical significance such as uncomplicated headache, nausea, vomiting, diarrhea, influenza, and accidental trauma (e.g. sprained ankle) which may interfere or prevent everyday life functions but do not constitute a substantial disruption

**e. Is a congenital anomaly/birth defect****f. Other situations:**

- Medical or scientific judgment should be exercised in deciding whether reporting is appropriate in other situations, such as important medical events that may not be immediately life-threatening or result in death or hospitalization but may jeopardize the subject or may require medical or surgical intervention to prevent one of the other outcomes listed in the above definition. These should also be considered serious.
- Examples of such events are invasive or malignant cancers, intensive treatment in an emergency room or at home for allergic bronchospasm, blood dyscrasias or convulsions that do not result in hospitalization, or development of drug dependency or drug abuse

**g. Is associated with liver injury and impaired liver function defined as:**

- $ALT \geq 3xULN$  and total bilirubin\*  $\geq 2xULN$  (>35% direct), **or**
- $ALT \geq 3xULN$  and  $INR^{**} > 1.5$ .

\* Serum bilirubin fractionation should be performed if testing is available; if unavailable, measure urinary bilirubin via dipstick. If fractionation is unavailable and  $ALT \geq 3xULN$  and total bilirubin  $\geq 2xULN$ , then the event is still to be reported as an SAE.

\*\* INR testing not required per protocol and the threshold value does not apply to subjects receiving anticoagulants. If INR measurement is obtained, the value is to be recorded on the SAE form.

Refer to [Appendix 2](#) for the required liver chemistry follow-up instructions

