#### Phase I/II liver chemistry stopping criteria and required follow up assessments

Liver Chemistry Stopping Criteria – Liver Stopping Event Subject with entry criteria ALT ≤ 2.5 x ULN	
ALT-absolute	ALT ≥ 5xULN
ALT Increase	ALT ≥ 3xULN persists for ≥4 weeks
Bilirubin	ALT ≥ 3xULN and bilirubin ≥ 2xULN (>35% direct bilirubin)
INR^2	ALT ≥ 3xULN and INR>1.5, if INR measured
Cannot Monitor	ALT ≥ 3xULN and cannot be monitored weekly for 4 weeks
Symptomatic	ALT ≥ 3xULN associated with symptoms (new or worsening) believed to be related to liver injury or hypersensitivity
Liver Chemistry Stopping Criteria – Liver Stopping Event Including subjects with documented liver metastases/tumor infiltration at baseline AND entry criteria ALT>2.5 x ULN but ≤5 x ULN	
ALT-absolute	Both ALT ≥ 5xULN and ≥2x baseline value
ALT Increase	Both ALT ≥ 3xULN and ≥ 1.5x baseline value that persists for ≥4 weeks
Bilirubin	ALT ≥ 3xULN and bilirubin ≥ 2xULN (>35% direct bilirubin)
INR^2	ALT ≥ 3xULN and INR>1.5, if INR measured
Cannot Monitor	Both ALT ≥ 3xULN and ≥ 1.5x baseline value that cannot be monitored for 4 weeks
Symptomatic	Both ALT ≥ 3xULN and ≥ 1.5x baseline value associated with symptoms (new or worsening) believed to be related to liver injury or hypersensitivity

Required Actions and Follow up Assessments following ANY Liver Stopping Event	
Actions	Follow Up Assessments

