
1. Serum bilirubin fractionation should be performed if testing is available. If serum bilirubin fractionation is not immediately available, discontinue study treatment for that subject if ALT  $\geq$  3xULN **and** bilirubin  $\geq$  2xULN. Additionally, if serum bilirubin fractionation testing is unavailable, **record presence of detectable urinary bilirubin on dipstick**, indicating direct bilirubin elevations and suggesting liver injury.
2. All events of ALT  $\geq$  3xULN **and** bilirubin  $\geq$  2xULN (>35% direct bilirubin) or ALT  $\geq$  3xULN **and** INR>1.5, if INR measured which may indicate severe liver injury (possible 'Hy's Law'), **must be reported as an SAE (excluding studies of hepatic impairment or cirrhosis)**; INR measurement is not required and the threshold value stated will not apply to subjects receiving anticoagulants
3. New or worsening symptoms believed to be related to liver injury (such as fatigue, nausea, vomiting, right upper quadrant pain or tenderness, or jaundice) or believed to be related to hypersensitivity (such as fever, rash or eosinophilia)
4. Includes: Hepatitis A IgM antibody; Hepatitis B surface antigen and Hepatitis B Core Antibody (IgM); Hepatitis C RNA; Cytomegalovirus IgM antibody; Epstein-Barr viral capsid antigen IgM antibody (or if unavailable, obtain heterophile antibody or monospot testing); Hepatitis E IgM antibody
5. If hepatitis delta antibody assay cannot be performed, it can be replaced with a PCR of hepatitis D RNA virus (where needed) [Le Gal, 2005].
6. Record the date/time of the PK blood sample draw and the date/time of the last dose of study treatment prior to blood sample draw on the CRF. If the date or time of the last dose is unclear, provide the subject's best approximation. If the date/time of the last dose cannot be approximated OR a PK sample cannot be collected in the time period indicated above, do not obtain a PK sample. Instructions for sample handling and shipping are in the Laboratory Manual.

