**Phase I/II Oncology liver chemistry increased monitoring criteria with continued therapy**

Liver Chemistry Increased Monitoring Criteria – Liver Monitoring Event	
Criteria	Actions

Subject with entry criteria ALT ≤ 2.5x ULN            ALT ≥ 3xULN but <5xULN and bilirubin <2xULN, without symptoms believed to be related to liver injury or hypersensitivity and who can be monitored weekly for 4 weeks
 
Subject with documented liver metastases/tumor infiltration at baseline AND entry criteria ALT > 2.5 x ULN but ≤ 5 x ULN            ALT ≥ 3x ULN and 1.5x baseline value but ALT <5x ULN and 2x baseline value and bilirubin <2xULN, without symptoms believed to be related to liver injury, or hypersensitivity and who can be monitored weekly for 4 weeks
	
 
Notify the GSK medical monitor within 24 hours of learning of the abnormality to discuss subject safety.
 
Subject can continue study treatment
 
Subject must return weekly for repeat liver chemistries (ALT, AST, alkaline phosphatase, bilirubin) until they resolve, stabilise or return to within baseline
 
If at any time subject meets the liver chemistry stopping criteria, proceed as described above
 
 
For subjects with entry criteria ALT ≤ 2.5 x ULN
 
 
If, after 4 weeks of monitoring, ALT <3xULN and bilirubin <2xULN, monitor subjects twice monthly until liver chemistries normalize or return to within baseline.
 
 
For subjects with documented liver metastases/tumor infiltration at baseline AND entry criteria ALT > 2.5 x ULN but ≤ 5 x ULN
 
 
If, after 4 weeks of monitoring, ALT <3xULN and <1.5x baseline value, and bilirubin <2xULN, monitor subjects twice monthly until liver chemistries normalize or return to within baseline
 

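### Subjects who keep dosing with ALT at or above 3×ULN are checked weekly without INR, and two appendices wrongly call INR not required, so the INR stopping criterion acts only on coagulation days or by discretion

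*Protocol*

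**What the plan says.** All references are to the current protocol (Amendment 4) unless stated.

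- **The criterion.** In both stopping tables of Appendix 3 (Section 14.3), ALT at or above 3×ULN together with "INR>1.5, if INR measured" is a liver stopping event. Footnote 2 there and Section 14.6.2 item g make the same combination an SAE.
- **Whether INR is required.** Footnote 2 adds "INR measurement is not required and the threshold value stated will not apply to subjects receiving anticoagulants". Item g adds "INR testing not required per protocol and the threshold value does not apply to subjects receiving anticoagulants".
- **The schedule.** Table 11 (Section 8.3.9) includes INR in the coagulation tests, and that section makes Table 11 tests mandatory on the Time and Events schedule. Table 8 places coagulation at screening, W1D1, W1D6, W2D1, W3D1, W5D1, W7D1, W9D1, every 4 weeks and end of treatment. Section 8 makes the schedule binding. SAP Section 11.6 also names INR among the coagulation results.
- **Monitoring on continued drug.** The increased-monitoring table in Appendix 3 lets a subject with entry ALT at or below 2.5×ULN stay on treatment with ALT from 3 to below 5×ULN, bilirubin below 2×ULN and no attributed symptoms. The instruction is: "Subject must return weekly for repeat liver chemistries (ALT, AST, alkaline phosphatase, bilirubin) until they resolve, stabilise or return to within baseline". The medical monitor must be told within 24 hours "of learning of the abnormality to discuss subject safety".
- **Liver-metastasis stratum (entry ALT above 2.5×ULN).** Weekly visits start at "ALT ≥ 3x ULN and 1.5x baseline value", whereas the INR criterion has no baseline condition.
- **Persistence stop.** This is "ALT ≥ 3xULN persists for ≥4 weeks" in the first stratum. In the liver-metastasis stratum ALT must also be "≥ 1.5x baseline value that persists for ≥4 weeks".

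**The concern.** A site that reads only the SAE definition or the Appendix 3 footnote is told that INR is optional, when the schedule makes it compulsory.

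The larger issue concerns subjects already past the ALT half of a stopping criterion and still taking drug. Their extra visits measure everything the liver rules need except INR. Under the conditional wording an unmeasured INR does not meet the criterion, so a site can follow the plan exactly and the INR stop cannot trigger between coagulation draws.

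If INR rises alone after ALT onset, it may be found late, or missed if it recovers before the next draw. Until it is measured the subject stays on drug and the matching SAE is not recorded.

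**Working it through.** The plan states no figure to reproduce. The check converts Table 8 to study days and overlays the weekly Appendix 3 visits.

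**1. Study days**, as (week − 1) × 7 + day:

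- Liver chemistry: 1, 6, 8, 13, 15, 22, 29, 43, 57, then every 28 days.
- Coagulation (INR): 1, 6, 8, 15, 29, 43, 57, then every 28 days.
- INR is drawn at 7 of the 9 liver-chemistry visits from W1D1 to W9D1 (not W2D6, day 13, or W4D1, day 22) and at every 4-weekly visit afterwards.

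**2. Gaps between scheduled INR draws:** 5, 2, 7, 14, 14, 14, then 28 days. The visit windows in Section 8.2.2 (±3 days to W9, ±5 to W52, ±7 after) could stretch these to 14 + 6 = 20, 28 + 10 = 38 and 28 + 14 = 42 days.

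**3. Weekly visits after ALT onset**, at +7, +14, +21 and +28 days, assuming onset is found at a scheduled liver-chemistry draw:

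| Onset (day) | Weekly visits (days) | With scheduled INR | Extra tubes if INR is added |
|---|---|---|---|
| W1D6 (6) | 13, 20, 27, 34 | none | 4 |
| W2D1 (8) | 15, 22, 29, 36 | 15, 29 | 2 |
| W2D6 (13) | 20, 27, 34, 41 | none | 4 |
| W3D1 (15) | 22, 29, 36, 43 | 29, 43 | 2 |
| W4D1 (22) | 29, 36, 43, 50 | 29, 43 | 2 |
| W5D1 (29) | 36, 43, 50, 57 | 43, 57 | 2 |
| W7D1 (43) | 50, 57, 64, 71 | 57 | 3 |
| W9D1 (57) | 64, 71, 78, 85 | 85 | 3 |

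For onset at W1D6 or W2D6 no weekly date coincides with a coagulation day, but scheduled INR still falls within 28 days, on days 8, 15 and 29 or on days 15 and 29. For onset at W9D1 or later, none of the visits at +7, +14 and +21 carries a scheduled INR. The next is at +28.

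**4. With INR in the weekly panel**, the longest required wait from onset is 7 days, against gaps of up to 14 days to W9D1 and 28 afterwards.

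**5. Liver-metastasis stratum.** Let B be baseline ALT in multiples of ULN. Since B > 2.5, 1.5B > 3.75, so weekly visits always start above the 3×ULN at which the INR criterion begins. The range with no weekly visit is 3 to below 1.5B: up to 3.9 at B = 2.6, 4.5 at B = 3 and 6.0 at B = 4. At B of 3 or more, the ALT half of the INR criterion is already met at entry. Drawing INR with every liver-chemistry sample would give gaps of 5, 2, 5, 2, 7, 7, 14, 14, then 28 days.

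**The case against.** **The contradiction is editorial.** Largely true. Section 8 and Section 8.3.9 govern, scheduled INR results still feed the stopping rule, and the footnote could mean only that INR need not be added for this criterion. Item g is harder to read that way, because it denies any protocol requirement.

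**INR was meant as a supplementary limb.** The conditional wording supports this, and no document requirement is breached. It does not explain why the limb is left unmeasured in the subjects it is meant to protect.

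**ALT detection usually comes with an INR.** True at most visits. After W9D1 the 28-day interval starts from a same-day INR. In the entry ALT ≤2.5×ULN stratum it ends when persistence stops drug anyway. That covers INR at onset, not a rise in the weeks between.

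**Other safeguards exist.** Bilirubin and symptoms are checked weekly, and the symptom list is broad. The medical-monitor call and the additional-test provisions in Sections 8.2, 8.3 and 14.6.5 permit INR, but none requires it. Table 12 does require INR in Grade 3 or 4 thrombocytopenia, but drug is then withheld.

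**Baseline-relative thresholds suit liver metastases.** Reasonable, and PT/INR had to be at or below 1.5×ULN at entry (Table 4). This part is therefore secondary.

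**The study has ended.** SAP Section 1 records early termination with 5 subjects enrolled. The value lies in the plan as written and in any reuse of this liver text.

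**Conclusion.** The concern holds as a modest safety-monitoring gap with a cheap remedy, plus a wording error. Between scheduled coagulation draws, the INR stopping and SAE criterion works only if INR is ordered at discretion. The documents give no frequency for the exposed case.

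Four stronger readings are not supported:

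- A reader might infer that INR goes unmeasured or that the liver rule is inoperative. Scheduled INR continues throughout, and the bilirubin, ALT and symptom criteria still operate.
- A reader might infer that the plan breaks its own rule. The criterion is conditional on measurement, so it is not broken.
- A reader might infer an effect on dose finding. The liver DLT in Table 3 has no INR component, so DLT counts and the MTD are untouched.
- A reader might infer that the weekly range is empty for high baselines in the liver-metastasis stratum. That requires ALT to be below both 5×ULN and twice baseline. The absolute stop needs both thresholds to be reached, so the monitoring range is more naturally its complement.

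The conclusion rests on nominal visit days and the text tables. Figures 3 and 4 and the Laboratory Manual are not available and could add an INR instruction.

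**What to change.** 1. Add INR to the weekly panel in the Appendix 3 increased-monitoring table. For onset at W1D6 or later this costs 2 to 4 extra local coagulation tubes per 4-week episode, at draws already being taken and only in subjects with ALT at or above 3×ULN.
2. In Appendix 3 footnote 2 and Section 14.6.2 item g, replace the statement that INR is not required with a pointer to Tables 8 and 11. Deleting the conditional phrase in the INR rows would not help on its own, because it changes nothing on days without an INR.
3. Correct item g's cross-reference from Appendix 2 (the ECOG scale) to Appendix 3.
4. Secondary and only partial: for liver-metastasis subjects with ALT at or above 3×ULN but below 1.5× baseline, draw INR with each scheduled liver-chemistry sample. This adds two tubes in all (W2D6 and W4D1) and splits the day 15 to 29 gap into two of 7 days. It leaves the 14-day gaps from W5D1 to W9D1 and the 28-day gaps afterwards.

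Items 2 and 3 cost only wording in an amendment.

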### 14.6.3. Definition of Cardiovascular Events

#### Cardiovascular Events (CV) Definition:

Investigators will be required to fill out the specific CV event page of the CRF for the following AEs and SAEs:

- Myocardial infarction/unstable angina
- Congestive heart failure
- Arrhythmias
- Valvulopathy
- Pulmonary hypertension
- Cerebrovascular events/stroke and transient ischemic attack
- Peripheral arterial thromboembolism
- Deep venous thrombosis/pulmonary embolism
- Revascularization

### 14.6.4. Recording of AEs and SAEs

#### AEs and SAE Recording:

- When an AE/SAE occurs, it is the responsibility of the investigator to review all documentation (e.g., hospital progress notes, laboratory, and diagnostics reports) relative to the event.
- The investigator will then record all relevant information regarding an AE/SAE in the CRF
- It is **not** acceptable for the investigator to send photocopies of the subject's medical records to GSK in lieu of completion of the GSK, AE/SAE CRF page.
- There may be instances when copies of medical records for certain cases are requested by GSK. In this instance, all subject identifiers, with the exception of the subject number, will be blinded on the copies of the medical records prior to submission of to GSK.
- The investigator will attempt to establish a diagnosis of the event based on signs, symptoms, and/or other clinical information. In such cases, the diagnosis will be documented as the AE/SAE and not the individual signs/symptoms.
- Subject-completed Value Evidence and Outcomes questionnaires and the collection of AE data are independent components of the study.
- Responses to each question in the Value Evidence and Outcomes questionnaire will be treated in accordance with standard scoring and statistical procedures detailed by the scale's developer.
- The use of a single question from a multidimensional health survey to designate a cause-effect relationship to an AE is inappropriate.

